7.4.2 Modifications of Study Therapy

7.4.2.1 Dose delays

A dose will be considered as actually delayed if the delay is exceeding 3 days (i.e., greater than or equal to 4 days from scheduled dosing date) for both nivolumab and BV. Participants may be dosed with nivolumab no less than 19 days from the previous dose.

The length of delay is defined as (duration of previous cycle in days - 21) for nivolumab or BV. Dose delays will be divided into following categories: on-time, 4-7 days, 8-14 days, 15-42 days, > 42 days. Reason for dose delay will be retrieved from CRF dosing pages.

The following parameters will be summarized by treatment group:

- Number of dose delayed per participant, Length of Delay and Reason for Dose Delay.

7.4.2.2 Infusion Modification

Each nivolumab or BV infusion can be interrupted and/or the IV infusion rate can be reduced. This information will be retrieved from CRF dosing pages.

The following parameters will be summarized by treatment group and drug:

- Number of participant with at least one dose infusion interrupted along with reason for the interruptions and number of infusions interrupted per participant.
- Number of participants with at least one infusion with IV rate reduced along with the reason of the rate reduction.

7.4.2.3 Dose Reductions

There will be no dose escalations or reductions of nivolumab allowed.

Only dose reduction of BV is permitted per protocol and should not be re-escalated without discussion with the sponsor.

Dose levels of BV are defined in the protocol as follows:

- Dose level 0. 1.8 mg/kg
- Dose level -1. 0.9 mg/kg

For any cycle (excluding Cycle 1), it will be defined as a dose reduction if the observed dose level (based on calculated administered dose) is below the dose level of the previously administered dose. Dose ranges for dose levels of BV are defined in Table 7.4.2.3-1.

Table 7.4.2.3-1: Calculated Dose Ranges and Related Dose Levels of Brentuximab

Dose Range (mg/kg)	Dose Level
≥ 1.35	Level 0
< 1.35	Level -1

The reason for dose reduction as reported by the investigator will be tabulated for all instances of dose reduction based on the Dose Change CRF page. A category ‘Unknown’ will be defined for all reductions with no reason reported by the investigator.

The following will be summarized of dose reduction for all treatment groups:

- Number and percentage of participants with at least one dose reduction and reason of the dose reduction by drug and treatment groups,
- Number and percentage of participants with a dose reduction to dose level -1 by drug and treatment groups,

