**Table 2-2: Procedural Outline During the Treatment Period (CA209812)**

Procedure	Cycle 1 Day 1 - Disease Progression or Unacceptable Toxicity	Notes  All windows proposed are calendar days. Procedures must be done within 72h prior to dosing unless otherwise specified. Dosing is to be performed every 3 weeks
Safety Assessments		
Targeted Physical Examination	X	Lymph node areas (for example, but not limited to, submandibular, cervical, supraclavicular, axillary, or inguinal lymph node), and abdominal organs (eg, spleen, liver)
Vital Signs	X	Includes body temperature, respiratory rate (RR), and seated blood pressure (BP) and heart rate.
Physical Measurements	X	Within 72 hours prior to dosing. Includes Weight and ECOG performance status ( Appendix 7 )
Adverse Events Assessment	Continuously	See Appendix 2/Section 9.2 . Assessed using NCI CTCAE v. 4.03.
Serious Adverse Events Assessment	Continuously	See Appendix 2/Section 9.2 . Assessed using NCI CTCAE v. 4.03
Review of Concomitant Medications	X	See section 7.7
Laboratory Tests	X	Within 72 hours prior to dosing to include CBC w/differential, AST, ALT, ALP, TBili, BUN or serum urea level, creatinine, Ca, Mg, Na, K, Cl, phosphate, LDH, glucose, amylase, lipase, c-reactive protein, albumin
Thyroid Function Testing	See note	TSH (reflex to free T3 and free T4 if abnormal result) to be performed every 9 weeks ( $\pm$ 7 days) from first dose regardless of dosing schedule.
Pregnancy Test for WOCBP	X See note	Serum or urine within 24 hours prior to first dose and then at least once every 4 weeks ( $\pm$ 7 days) regardless of dosing schedule.
Efficacy Assessments		
Radiographic Tumor Assessment FDG-PET-CT or PET-MRI scans from vertex to toes	See note	FDG PET-CT or PET-MRI will be performed at the end of cycle 5, 10, 15, and every 5 cycles until disease progression. FDG PET-CT or PET-MRI can be performed as clinically warranted for suspicion of recurrence during the non-protocol specified time points
B symptoms	See note	Collected Day 1 (prior to dosing) of every other cycle (cycle 1, 3, etc)

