### **Nivolumab and Brentuximab vedotin arm**

Participants should receive nivolumab at a dose of 360 mg as a 30-minute infusion on Day 1 of each treatment cycle until progression, unacceptable toxicity, withdrawal of consent, or the study ends, whichever occurs first. No dose escalations or reductions of nivolumab are allowed. Premedications are not recommended for the first dose of nivolumab. For 30-minute infusions, infusion durations are  $\pm 5$  minutes. For Q3W dosing cycles, participants may be dosed within a  $\pm 3$  day window.

For participants in the nivolumab/BV arm, BV will be administered first as a 30-minute infusion followed by a minimum 30-minute rest prior to the nivolumab infusion. Brentuximab vedotin will be administered as a 1.8 mg/kg dose on Day 1 of each treatment cycle every 3 weeks for 16 cycles. In the absence of infusion-related reactions, the infusion rate for all participants should be calculated in order to achieve a 30-minute infusion period. Brentuximab vedotin must not be administered as an IV push or bolus nor mixed with other medications. Dosing of BV is based on participant's actual body weight. Doses must be adjusted for participants who experience a  $\geq 10\%$  change in weight from baseline. Other dose adjustments for changes in body weight are permitted per institutional standard. An exception to weight-based dosing is made for participants weighing greater than 100 kg; doses will be based on 100 kg for these individuals. Rounding is permissible within 5% of the nominal dose.

Nivolumab Injection, 100 mg/10 mL (10 mg/mL) is to be administered as an IV infusion through a 0.2-micron to 1.2-micron pore size, low-protein binding in-line filter at the protocol-specified doses. It is not to be administered as an IV push or bolus injection. Nivolumab injection can be infused undiluted (10 mg/mL) or diluted with 0.9% Sodium Chloride Injection, USP or 5% Dextrose Injection, USP to protein concentrations as low as 1 mg/mL. Instructions for dilution and infusion of nivolumab injection may be provided in the clinical protocol, pharmacy binder, or pharmacy reference sheet. Care must be taken to assure sterility of the prepared solution as the product does not contain any antimicrobial preservative or bacteriostatic agent.

Nivolumab infusions are compatible with polyvinyl chloride (PVC) or polyolefin containers and infusion sets, and glass bottles.

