### **7.4.2 Brentuximab vedotin**

The recommended dose modifications for BV treatment associated toxicity are provided in [Table 7.4.2-1](#). Doses reduced for BV-related toxicity should not be re-escalated without discussion with the sponsor. Dose escalation of BV beyond 1.8 mg/kg is not permitted. Dose reductions below 1.2 mg/kg are not allowed.

If BV treatment is delayed for any reason, other treatments must be continued. Participants who require delay of BV should be re-evaluated frequently and BV dosing resumed when re-treatment criteria are met. Dose delays of more than 3 weeks may be allowed after discussion with the study medical monitor.

Recommendations for management of infusion related reactions due to BV are described in [Section 7.1.5](#).

Participants who discontinue nivolumab treatment due to a treatment-related AE may continue treatment with BV for a maximum of 16 cycles, or until disease progression or unacceptable toxicity, whichever occurs first. Participants who discontinue BV due to a treatment-related AE may continue to receive nivolumab treatment until disease progression or unacceptable toxicity.

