**Table 7.4.2-1: Dose Modifications for Brentuximab Vedotin**

Toxicity	Grade 1	Grade 2	Grade 3	Grade 4
Peripheral Neuropathy	Continue at same dose level	Hold until peripheral neuropathy resolves to $\leq$ Grade 1 and then resume treatment at 1.2 mg/kg a	Withhold (delay) until toxicity resolves to $\leq$ Grade 2 or baseline, then resume treatment at 1.2 mg/kg or discontinue if reduction has already occurred.	Discontinue treatment
Non-hematologic (except peripheral neuropathy)	Continue at same dose level	Continue at same dose level	Withhold (delay) dose until toxicity is $\leq$ Grade 2 or has returned to baseline, then resume treatment at the same dose level b	Withhold dose until toxicity is $\leq$ Grade 2 or has returned to baseline, then reduce dose to 1.2 mg/kg and resume treatment, or discontinue at the discretion of the investigator a,b,c
Hematologic d	Continue at same dose level	Continue at same dose level	Withhold (delay) until toxicity resolves to $\leq$ Grade 2 or baseline, then resume treatment at the same dose level. c Growth factor support (G-CSF or GM-CSF) should be considered for subsequent cycles. If Grade 4 neutropenia recurs despite growth factor support, consider discontinuation.	Discontinue treatment

a Dose reductions below 1.2 mg/kg are not allowed, and toxicities should be managed with dose delays

b Participants who develop Grade 3 or 4 electrolyte laboratory abnormalities may continue study treatment without dose delay

c Treatment should be discontinued for participants who experience Grade 4 infusion-related reactions.

d Support with blood product transfusions allowed per institutional standard of care.

e Participants who develop Grade 3 or 4 lymphopenia may continue study treatment without dose delay.

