7.4.1 Administration of study therapy

The following parameters will be summarized (descriptive statistics) by drug (nivolumab or BV) and treatment group:

- Relative dose intensity (%) using the following categories: < 50%; 50 - < 70%; 70 - < 90%; 90 - < 110%; $\geq 110\%$.
- Number of doses received for each drug (summary statistics).
- Cumulative dose
- Number of cycles received.

Duration of treatment will be presented by treatment group using a Kaplan-Meier curve whereby the last dose date will be the event date for those participants who are off study therapy. Median duration of treatment and associated 95% CI will be provided. Participants who are still on study therapy will be censored on their last dose date.

A by-participant listing of dosing of study medication (record of study medication, infusion details, and dose change) and a listing of batch number will be also provided.

Below table summarizes the key parameters used to calculate dosing data.

Table 7.4.1-1: Administration of study therapy: definition of parameters

	Nivolumab	BV
Dosing schedule per protocol	360mg every 3 weeks	1.8 mg/kg every 3 weeks
Dose	Dose (mg) is defined as Total Dose administered (mg). Dose administered in mg at each dosing date on the CRF.	Dose (mg/kg) is defined as Total Dose administered (mg) / most recent weight (kg). Dose administered in mg at each dosing date and weight are collected on the CRF.
Cumulative Dose	Cum dose (mg) is sum of the doses (mg) administered to a participant during the treatment period.	Cum dose (mg/kg) is sum of the doses (mg/kg) administered to a participant during the treatment period.
Relative dose intensity (%)	$\text{Cum dose (mg)} / [(\text{Last dose date} - \text{Start dose date} + 21) \times 360 / 21] \times 100$	A: $\text{Cum dose (mg/kg)} / [(\text{Last dose date} - \text{Start dose date} + 21) \times 1.8 / 21] \times 100$
Duration of treatment	Last dose date - Start dose date +1	Last dose date - Start dose date +1

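### The SAP takes the reduced BV dose as 0.9 mg/kg where the protocol sets 1.2 mg/kg, and its 1.35 mg/kg cut-off falls inside the range of compliant reduced doses

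*SAP*

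**What the plan says.** SAP 7.4.2.3 introduces its two BV levels with "Dose levels of BV are defined in the protocol as follows". It gives level 0 as 1.8 mg/kg and then "Dose level -1. 0.9 mg/kg". Table 7.4.2.3-1 classes a calculated dose of 1.35 mg/kg or more as level 0 and anything lower as level -1. From Cycle 2 on, a reduction is a dose whose level is below that of the dose given before it. SAP 7.4.1 calculates the dose as milligrams given divided by the most recent weight.

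Protocol 7.4.2 states "Dose reductions below 1.2 mg/kg are not allowed". Protocol Table 7.4.2-1 uses 1.2 mg/kg wherever it calls for a lower dose; for Grade 3 neuropathy, for example, it says "resume treatment at 1.2 mg/kg or discontinue if reduction has already occurred". A footnote to the table repeats the floor.

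Protocol 7.1 sets how the milligram amount may depart from the nominal dose, with the same terms in both arms:
- "Rounding is permissible within 5% of the nominal dose".
- Re-dosing is compulsory only once weight has changed by 10% or more from baseline.
- Below that, "Other dose adjustments for changes in body weight are permitted per institutional standard".
- Participants above 100 kg are dosed as if they weighed 100 kg.

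**The concern.** The SAP credits the protocol with a dose that the protocol prohibits. Nothing in the documents explains 0.9 as a leftover: the protocol's summary of key changes lists no change to BV dose levels.

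The label matters because the SAP asks for the number and percentage of participants reduced to level -1. Read against the SAP's own definition, that is a 50% cut (1 - 0.9/1.8). The reduction the protocol prescribes is 33% (1 - 1.2/1.8).

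The cut-off matters because it decides which doses count as reductions. Neuropathy is a notable BV toxicity (Protocol 3.3) and is one of the triggers for the 1.2 mg/kg dose. With no formal testing planned for 23 participants (Protocol 10), descriptive tables such as these carry much of the report.

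**Working it through.** **Inputs.** Levels 1.8 and 0.9 mg/kg and cut-off 1.35 mg/kg (SAP 7.4.2.3); calculated dose = mg / most recent weight (SAP Table 7.4.1-1); reduced dose 1.2 mg/kg (Protocol 7.4.2 and Table 7.4.2-1); rounding of up to 5% either way, compulsory re-dosing at a 10% weight change, and the 100 kg cap (Protocol 7.1).

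**1. The SAP's cut-off.** (1.8 + 0.9)/2 = 1.35, an exact match. The SAP does not say how it chose 1.35, so this origin is inferred. With the protocol's dose the midpoint is (1.8 + 1.2)/2 = 1.50.

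**2. What a compliant dose can read (up to 100 kg, or with weight capped).** Lowest = nominal × 0.95/1.10; highest = nominal × 1.05/0.90. The weight limits are approached but not reached, since a 10% change forces re-dosing.

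| Nominal dose | Lowest | Highest |
|---|---|---|
| 1.2 mg/kg | 1.036 | just under 1.400 |
| 1.8 mg/kg | 1.555 | just under 2.100 |

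The cut-off of 1.35 lies inside the first range. A cut-off of 1.5 lies in the gap between the two.

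**3. What it takes to reach 1.35 on a reduced dose.**
- Rounding alone: 1.2 × 1.05 = 1.26. Not reached. This is also the highest reading where the site doses on current weight.
- Weight loss alone: just under 1.2/0.90 = 1.333. Not reached.
- Both: with the full 5% rounding, the loss must be at least 1 - 1.26/1.35 = 6.67%. With a loss just under 10%, rounding up must exceed about 1.35 × 0.90/1.2 - 1 = 1.25%.

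**4. Error (a): a reduction missed or dated late.** Baseline weight is 80 kg. Weight has already fallen to 74 kg (-7.5%, no compulsory re-dosing) when the first reduced dose is ordered on baseline weight: 1.2 × 80 = 96 mg, rounded to 100 mg (100/96 - 1 = +4.2%). The calculated dose is 100/74 = 1.351, which is level 0, so no reduction is recorded. If a later reduced dose reads below 1.35, the reduction is recorded then, at the wrong cycle. It is missed altogether only if every later reduced dose also reads 1.35 or more. The order of events is essential: had the first 100 mg dose been given at 80 kg, it would read 100/80 = 1.25 and be flagged at once.

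**5. Error (b): a reduction counted that did not happen.** The same participant stays on 100 mg at 75, 74 and then 75 kg. The readings are 1.333, 1.351 and 1.333, that is, level -1, level 0, level -1. The last step meets the SAP's rule for a reduction although the milligram dose never changed. The count of participants with at least one reduction is not inflated, but a derived count of instances is.

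**6. The 100 kg cap.** A full capped dose is 1.8 × 100 = 180 mg. On uncapped weight it reads below 1.35 above 180/1.35 = 133 kg, and below 1.5 above 180/1.5 = 120 kg. This does not come from the 0.9 figure, but it decides whether a 1.5 cut-off works. On capped weight, a grid over baselines of 40 to 200 kg, weight change just under 10% either way and rounding of 5% either way gave 1.036-1.400 for reduced doses and 1.555-2.100 for full doses.

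**The case against.** The strongest reply is that the mismatch has almost no practical effect, and most of that reply stands.

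- A dose of exactly 1.2 mg/kg is below 1.35 and is counted as a reduction.
- Neither rounding nor weight loss alone reaches 1.35. BV dosing is on actual body weight, and weight is taken at each dosing visit ("Within 72 hours prior to dosing. Includes Weight and ECOG performance status"), so sites that use it produce no misses.
- Up to 100 kg, no compliant full dose is misread as reduced.
- There are other records. The SAP provides "A by-participant listing of dosing of study medication", which covers dose changes and can be read in full for 23 participants; the investigator's reason comes from the Dose Change CRF page; and Protocol 7.4 asks sites to contact the medical monitor whenever a dose is reduced.
- Table layouts are in a separate Data Presentation Plan (SAP 9), so it is not known whether 0.9 mg/kg would be printed anywhere.

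These points bear on how often the error would show. They leave untouched the contradiction between the documents and the placing of the cut-off within the compliant reduced range.

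A reader might go further and infer that reductions in general will be misclassified, that participants might be dosed at 0.9 mg/kg, or that exposure or efficacy results are compromised. The documents support none of these. Misclassification needs the combination in step 3. The SAP section is a reporting rule and gives sites no dosing instruction. Relative dose intensity is calculated against 1.8 mg/kg without using the level table, and efficacy, alpha and sample size do not depend on it.

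**Conclusion.** Wrong as written; minor, at the low end. That the SAP and protocol give different reduced doses is certain from the text. That 1.35 mg/kg lies inside the compliant reduced range follows from the protocol's rounding and weight rules and the SAP's formula, whatever the origin of 1.35.

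The number of misclassified reductions cannot be estimated: the documents do not say how many participants were reduced, how their weights changed, or which weight sites dosed on. A miss needs upward rounding and a weight loss of about 6.7% to just under 10%, both in place at the first reduced dose, and every later reduced dose at 1.35 or above. The likely number is zero or very few of 23. The effect is confined to the descriptive dose-reduction tables. The weight-cap problem arises under the present cut-off only above 133 kg, and no participant weights are given.

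**What to change.** Make three changes to SAP 7.4.2.3 together:
1. Set dose level -1 to 1.2 mg/kg.
2. Set the cut-off in Table 7.4.2.3-1 to 1.5 mg/kg. Both examples above then class correctly, since 1.333 and 1.351 are below 1.5.
3. Classify dose level on weight capped at 100 kg, as the protocol doses. Without the cap, moving to 1.5 would lower the weight at which a full 180 mg dose is misread from 133 kg to 120 kg.

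The cost is two lines of SAP text, one programming constant and one weight cap. No new data are needed, and Protocol 10.3 has the SAP finalised before database lock, so the correction fits the planned process.

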7.4.3 Concomitant Medications

Concomitant medications, defined as medications other than study medications which are taken at any time on-treatment (i.e. on or after the first day of study therapy and within 100 days following the last dose of study therapy), will be coded using the WHO Drug Dictionary.

The following summary tables will be provided:

- Concomitant medications (participants with any concomitant medication, participants by medication class and generic term).

A by-participant listing will accompany the table.

7.4.4 Discontinuation of Study Therapy

The number and percentage of participants who have discontinued all study treatment and reason for discontinuation will be summarized by treatment group and overall using participant status eCRF page from end of treatment. This summary, unlike other safety analyses, will include all randomized participants and will be grouped by treatment group as randomized. This is done in order to give a full accounting of all participants who are off study treatment, including those who were randomized but never treated.

7.5 Efficacy

7.5.1 Primary analysis of PFS by BICR

The primary endpoint PFS assessed by BICR will be compared between the two randomized arms using a two-sided, log-rank test stratified by the same factors in the randomization. An O'Brien and Fleming α spending function will be employed to determine the significance levels and stopping boundaries at the interim look (overall $\alpha=0.05$).

HR and corresponding two-sided 100 (1- α)% (α adjusted for the interim analysis) and 95% CI will be estimated in a stratified Cox proportional hazards model using randomized arm as a single covariate. The PFS curves for each treatment group will be estimated using the KM product-limit method. Two sided, 95% confidence intervals for median PFS will be constructed based on a log-log transformed CI for the survivor function S(t).

PFS rates at 6 months will be estimated using KM estimates on the PFS curve. PFS rates at 12, 18, 24, 36 months may also be estimated depending on whether minimum follow-up will be longer than or equal to timepoint to generate the rate. Associated two-sided 95% CIs will be calculated.

The source of PFS event (death vs. progression) will be summarized by treatment group. The status of participants who are censored in the PFS Kaplan-Meier analysis will be tabulated for each treatment group using following categories:

- Never treated
- On-study (on treatment or progression-free in follow-up).
- Off-study: (lost to follow-up, withdraw consent other).
- Received subsequent anti-cancer therapy.

To examine the assumption of proportional hazards in the Cox regression model, in addition to treatment, a time-dependent variable defined by treatment by time (log time) interaction will be added into the model. A two-sided Wald Chi-square p-value of less than 0.1 may indicate a potential non-constant treatment effect. [REDACTED]

7.5.1.1 Sensitivity analyses of PFS

Sensitivity analyses of PFS will also be performed as described below. Median PFS, HR (95% CIs), p-value from the log-rank test will be computed as in the primary PFS analysis

- *PFS accounting for assessment after subsequent therapy* participants will be defined similarly to the primary definition except that events (progression or death) and tumor assessments that occurred after subsequent anticancer therapy will be taken into account. A Kaplan-Meier plot will be produced

Table 7.5.1.1-1: Censoring scheme 1 for Sensitivity Analysis of PFS

Situation	Date of Progression or Censoring	Outcome
No baseline tumor assessments	Randomization date	Censored
No on-study tumor assessments and no death	Randomization date	Censored
New subsequent anticancer treatment started without a prior reported progression by BICR or death	Date of last evaluable tumor assessment prior to or on the date of initiation of the subsequent anti-cancer therapy	Censored
Progression per BICR documented at a scheduled or unscheduled visit and no other subsequent anticancer treatment started before progression	Date of the first documented tumor progression	Progressed
Participant progression free, no death and no subsequent anti-cancer therapy treatment started	Date of last evaluable tumor assessment	Censored
Death without prior progression per BICR	Date of death	Progressed

- PFS accounting for missing tumor assessment prior to PFS event (progression or death)*. This analysis will be performed only if at least 20% of events have missing prior tumor assessment. It will apply the following restriction to the primary definition: If the elapsed time between the PFS event and the last on-study tumor assessment immediately prior to the event (or randomization date if no on-study scan) is two or more missed visits (more than 12 weeks + 10 days), the participant will be censored at his last tumor assessment prior to the PFS event (or randomization date if no on-study scan). A Kaplan-Meier plot will be produced.

Table 7.5.1.1-2: Censoring scheme 2 for Sensitivity Analysis of PFS

Situation	Date of Progression or Censoring	Outcome
No baseline tumor assessments	Randomization date	Censored
No on-study tumor assessments and no death	Randomization date	Censored
New subsequent anticancer treatment started without a prior reported progression by BICR or death	Date of last evaluable tumor assessment prior to or on the date of initiation of the subsequent anti-cancer therapy	Censored
Progression per BICR documented at a scheduled or unscheduled visit and no other subsequent anticancer treatment started before progression	Date of the first documented tumor progression	Progressed
Participant progression free, no death and no subsequent anti-cancer treatment started	Date of last evaluable tumor assessment	Censored
Death without prior progression per BICR and no subsequent anti-cancer therapy treatment started	Date of death	Progressed

Death or progression after two or more missed visits	Date of last tumor assessment prior to the PFS event	Censored
---	---	-----------------

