### 10.3.1 Efficacy Analyses

Endpoint	Statistical Analysis Methods
Primary	
The primary endpoint, PFS based on investigator assessment, will be compared in two randomized arms via a two-sided, log-rank test stratified by the same factors used in randomization. Participants who die without a reported progression will be considered to have progressed on the date of their death. Participants who did not progress or die will be censored on the date of their last tumor assessment. Participants who did not have any on study assessments and did not die will be censored on the randomization date. A participant who initiates a subsequent anti-cancer therapy will be censored on the date of last tumor assessment prior or on the start date of their subsequent anti-cancer therapy. Sensitivity analyses will be performed using different PFS definitions to assess the robustness of the primary analysis. The PFS curve, median and PFS rate at 6, 12, 18, and 24 months for each randomized arm will be estimated using the Kaplan-Meier product-limit method. Two sided, 95% confidence intervals for median PFS will be computed by Brookmeyer and Crowley method. A two-sided, 95% confidence interval for the PFS rates will be computed by Greenwood method. The hazard ratio (HR) and corresponding two-sided <math>100 * (1-\alpha)\%</math> (<math>\alpha</math> adjusted for the interim analysis) confidence interval will be estimated in a Cox proportional hazards model using randomized arm as a single covariate, stratified by the same factors used in randomization.

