4 ENDPOINTS

4.1 Primary Endpoints

Progression Free Survival (PFS)

Progression-free Survival (PFS) by BICR: defined as time from date of randomization to the date of death due to any cause or the first documented disease progression as determined by the BICR, whichever occurs first.

Participants who die without a reported progression will be considered to have progressed on the date of their death. Participants who did not progress or die will be censored on the date of their last tumor assessment. Participants who did not have any on study assessments and did not die will be censored on the randomization date. A participant who initiates a subsequent anti-cancer therapy (including allogeneic transplant) will be censored on the date of last tumor assessment prior or on the start date of their subsequent anti-cancer therapy.

The censoring scheme is summarized in Table 4.1-1.

Table 4.1-1: Censoring scheme used in primary analysis of PFS

Situation	Date of Progression or Censoring	Outcome
No baseline tumor assessments	Randomization date	Censored

No on-study tumor assessments and no death	Randomization date	Censored
New subsequent anticancer therapy started without a prior reported progression by BICR or death	Date of last evaluable tumor assessment prior to or on the date of initiation of the subsequent anti-cancer therapy	Censored
Progression per BICR documented at a scheduled or unscheduled visit and no other subsequent anticancer therapy started before	Date of the first documented tumor progression	Progressed
Participant progression free, no death and no subsequent anti-cancer therapy started	Date of last evaluable tumor assessment	Censored
Death without prior progression per BICR and no subsequent anticancer therapy started	Date of death	Progressed

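### SAP 7.5.1.1: the censoring table for PFS sensitivity analysis 1 excludes the post-switch progressions and scans that its own text says will count

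*SAP*

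**What the plan says.** The primary PFS scheme (SAP 4.1, Table 4.1-1) censors a participant who starts subsequent anticancer therapy before progression or death at the latest evaluable scan up to that start. Its death row applies to "Death without prior progression per BICR and no subsequent anticancer therapy started".

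SAP 7.5.1.1 then sets out two sensitivity analyses. By its title, the first is about assessments made after subsequent therapy. Its text keeps the primary definition "except that events (progression or death) and tumor assessments that occurred after subsequent anticancer therapy will be taken into account". Its table, Table 7.5.1.1-1, has these rows:

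- Row 3: "New subsequent anticancer treatment started without a prior reported progression by BICR or death" is censored at the latest evaluable scan up to the start of that treatment.
- Row 4: the event row for progression is "Progression per BICR documented at a scheduled or unscheduled visit and no other subsequent anticancer treatment started before progression".
- Row 5: the last-scan censoring row is "Participant progression free, no death and no subsequent anti-cancer therapy treatment started".
- Death row, in italics: "Death without prior progression per BICR" is an event at the date of death.

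The second analysis (Table 7.5.1.1-2) concerns missed visits. It keeps the primary handling of subsequent therapy, including in its death row: "Death without prior progression per BICR and no subsequent anti-cancer therapy treatment started".

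Protocol 10.3.1 states the purpose: "Sensitivity analyses will be performed using different PFS definitions to assess the robustness of the primary analysis".

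**The concern.** The text and the table give different definitions of one analysis. The text counts three kinds of information after a switch to new therapy: progressions, deaths and scans. The table admits at most one of them, deaths. A programmer working from the table would produce a different analysis from one working from the text, and the SAP does not say which governs.

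Censoring at subsequent therapy is a natural target for a robustness check, because participants who switch before documented progression may not have the same prognosis as those who do not. Analysis 1 is the only PFS sensitivity analysis aimed at that rule. If the table is followed, the check on post-switch progression is never made, although the report would carry a title saying that it was.

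**Working it through.** No figure in the plan needs reproducing. The check compares the two tables row by row and then applies each rule to simple patient histories.

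**Row comparison, Table 4.1-1 against Table 7.5.1.1-1**

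- Rows 1 and 2 (no baseline scan; no on-study scan and no death): same.
- Row 3 (switch without prior progression or death): same censoring rule and date.
- Row 4 (progression): same condition that no new therapy came first.
- Row 5 (no progression, death or new therapy): same.
- Death row: the condition that no new therapy was started is dropped. This is the only change of substance.

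**Applied to histories.** Times are hypothetical months, chosen only to exercise the rules. In (a) to (d) the participant switches at month 6 without prior progression; in (e) and (f) there is no switch.

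| History | Text of 7.5.1.1 | Table 7.5.1.1-1 | Table 4.1-1 (primary) |
|---|---|---|---|
| (a) Progression at 9, alive | Event at 9 | Censored at last scan up to 6 | Censored, same date |
| (b) Progression at 9, death at 12 | Event at 9 | Censored at last scan up to 6, or event at 12 | Censored |
| (c) Death at 10, no progression | Event at 10 | Row 3 censors; death row gives event at 10 | Censored |
| (d) Later scans, no event | Censored at last scan, including those after 6 | Censored at last scan up to 6 | Censored, same date |
| (e) Progression at 9 | Event at 9 | Event at 9 | Event at 9 |
| (f) Death at 10 | Event at 10 | Event at 10 | Event at 10 |

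**Reading the results**

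- In (a) and (b) no reading of the table gives the text's answer. In (d) it fails whenever a post-switch scan exists.
- In (b) the table's answer depends on whether a progression after the switch counts as a prior progression in the death row. If it does, the death row does not apply and row 3 censors. If it does not, row 3 and the death row both apply.
- In (c) both rows apply and no order is stated. If the death row wins, table and text agree. If row 3 wins, the table gives the primary result.
- The table can therefore depart from the primary scheme only through deaths after a switch, and only if the death row overrides row 3.

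**Size.** Let S be the number of participants who switched without prior progression. Only they can be classified differently by text and table, and each contributes at most one event. The number affected, D, satisfies 0 ≤ D ≤ S ≤ 23, because 23 were randomized (Protocol 10). S is not given.

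**The case against.** The strongest reply is that the intent is clear and little now depends on it. The title and the text agree with each other. The italics on the death row suggest that it was meant to override row 3. Protocol 10 says that no formal testing will be done and that previously planned analyses will be run only if appropriate, so analysis 1 may never be run. SAP 7.1 already makes p-values from sensitivity analyses descriptive. Protocol Table 2-3 stops scans for participants who discontinue treatment before progression, so few post-switch progressions or scans may exist. Other outputs also show part of the picture: SAP 7.5.1 tabulates participants censored for subsequent therapy, SAP 7.5.3.2 summarizes and lists those therapies, and the OS analysis has no censoring at subsequent therapy, so it captures post-switch deaths that are recorded.

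Most of this stands as an argument about weight. It does not remove the contradiction. The italics support reading the table as deliberately edited to add deaths only, which is not what the text says, and no other section settles the matter. The other outputs show how much censoring occurred but do not re-estimate PFS without it. Some post-switch data may exist: the Synopsis (Overall Design) and Protocol 5.1 still describe following participants who stop before progression for progression and then survival, so those who stopped before Revised Protocol 01 may have later records. Neither place says that scanning continues after a new therapy starts.

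A reader might go further and infer that analysis 1 simply duplicates the primary analysis. The documents do not support that as a flat statement. It is true only if row 3 overrides the death row, and the text and italics point the other way.

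**Conclusion.** The point holds as an internal contradiction in the SAP. The text of analysis 1 counts progressions, deaths and scans after subsequent therapy; the table never counts a post-switch progression or uses a post-switch scan, and is at most a check on post-switch deaths. This follows from the wording of the rows alone and needs no assumption about the data.

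The consequence is small. It concerns between 0 and S of 23 participants, in an analysis that is descriptive and may not be run. A reader might infer a material threat to the trial's PFS conclusion, or want to turn the defect into an expected number of misclassified events. The documents support neither. No inferential conclusion is planned, and neither S nor the length of observation after a switch is given. Follow-up now ends at a visit timed from the last dose, not from the switch, under a schedule that also stops scans after discontinuation before progression. The point deserves correction because the SAP otherwise yields two different classifications of the same participant, not because the result is likely to move.

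**What to change.** Preferred: make Table 7.5.1.1-1 match the text and title. Delete row 3. Remove the no-subsequent-therapy condition from rows 4 and 5. Keep rows 1 and 2 and the death row as they are. Histories (a) and (b) then become events at 9, (c) an event at 10, and (d) is censored at the last evaluable scan whenever taken. With row 3 gone, no precedence sentence is needed for its conflict with the death row. A blanket rule that death takes precedence should be avoided, because it would also override row 1 and make this analysis differ from the primary for reasons unrelated to subsequent therapy.

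Alternative, if only post-switch deaths were intended: keep the table and rewrite the text and title to say so. State that the death row overrides row 3 only, and say whether a progression after the switch counts as a prior progression.

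The cost is low: three row edits, or a short rewrite of the text with two clarifications, and no new data. The SAP is still version 1.0 of 24-Feb-17 and refers to central review (BICR), while Revised Protocol 01 bases PFS on investigator assessment. The three BICR references in this table must change anyway, so both edits can be made together.
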